### 8.6.2 Prior and Concomitant Medications

All medications and other treatments taken by the patient prior to the start of the study at screening and treatments initiated during the study, must be recorded on the eCRF. The entry must include the dose, regimen, route, indication, and dates of use.

After the baseline visit, medication to treat minor illness(es) are generally permitted, including:

- Use of localized palliative radiation for pre-existing lesions to control pain, at the discretion of the physician.
- Corticosteroids use: topical, inhaled, ophthalmologic, intra-articular, or intranasal corticosteroids; systemic steroids at physiologic doses not to exceed 10 mg/day of prednisone or equivalent. For management of side effects including nausea or infusion reactions, intermittent prophylactic or therapeutic use of glucocorticoids is allowed at doses required for medical therapy administered according to institutional standard of care and at the Investigator's discretion.

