### 8.6.3 Prohibited Medications

If there is a clinical indication for the use of one of the following prohibited medications, then discontinuation from the study drug may be required.

- Anti-neoplastic therapy, whether approved or experimental, including but are not limited to: chemotherapy, immunotherapy, surgery, radiotherapy are not allowed with OBI-999. **NOTE:** Use of localized palliative radiation for pre-existing lesions to control pain may be allowed at the discretion of the physician.
- Immunosuppressive therapy (e.g., cyclosporine, rapamycin, tacrolimus, cyclophosphamide, methotrexate, etc.).
- Systemic steroids of >10 mg/day prednisone or equivalent
- Any other concurrent investigational therapy, regardless of indication.
- Strong inhibitors or inducers of CYP3A (see [Appendix 2](#))
- Clinical inhibitors of P-glycoprotein (see [Appendix 3](#))

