p. Radiology (CT or MRI scan) evaluations of tumor response: Performed during screening and during the study every 6 weeks for the first 3 months, and then every 9 weeks until discontinuation of study treatment, disease progression, death, or initiation of further systemic cancer therapy, including radiation therapy, whichever occurs earlier. CT or MRI scan will be performed within 1 week prior to the start of the next cycle. Unscheduled scan can be performed anytime, if needed to confirm disease progression. Radiology assessment for early termination/end of study, should ONLY be performed if  $\geq 9$  weeks have passed from the previous scheduled CT/MRI scan. Same assessment method and same technique should be used on each patient while on study.

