## **10 Clinical Activity Profile Assessments**

Radiology (CT or MRI scan) evaluations ( $\pm 7$  days) of tumor response are to be performed during screening within 28 days prior to Cycle 1 Day 1 (first dose of study medication), and thereafter during the study every 6 weeks for the first 3 months and then every 9 weeks until discontinuation of study treatment, disease progression, death, or initiation of further systemic cancer therapy, including radiation therapy. Radiology assessment for end of study follow-up and early termination should be performed unless the patient already has radiographic confirmation of progressive disease  $\leq 9$  weeks prior to permanent discontinuation of study drug. The same assessment method and the same technique should be used on each patient while on study.

An end-of-treatment radiology assessment should be performed unless the patient already has radiographic confirmation of progressive disease  $\leq 9$  weeks prior to permanent discontinuation of study drug. The same assessment method and the same technique should be used on each patient while on study.

Overall tumor response and progression will be evaluated by the Investigator according to RECIST 1.1.

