- Any \geq Grade 3 non-hematological toxicity (except Grade 3 fatigue, nausea, vomiting, or diarrhea lasting $<$ 24 hours with optimal therapy, Grade 3 non-hematologic laboratory abnormalities that resolve to Grade 1 or baseline within 14 days).

All TEAEs, unless they are determined to be not related to study drug will be taken into consideration in determining DLTs. The period for DLT observation is 21 days from the start of first dose of OBI-999 (i.e., Day 1).

DLTs (not to be programmatically derived; will be analyzed as collected on eCRF) will be displayed by dose level in a frequency table in decreasing order of incidence. AEs will be graded according to the NCI CTCAE V5.0. All TEAEs unless they have been determined to be not related to study drug will be DLTs and will be summarized by dose, SOC and PT. A listing of DLTs will be prepared.

C. MTD and RP2D of OBI-999

At the time of this version of the SAP, Part A (Dose-Escalation) was completed. The RP2D of 1.2 mg/kg was identified during SRC review.

PART B (COHORT-EXPANSION)

A. Objective Response*

Overall tumor response (not to be programmatically derived; will be analyzed as collected on eCRF) will be listed by cancer type and visit. For each patient, best overall response (BOR) is defined as the best overall tumor response (complete response [CR], partial response [PR], stable disease [SD], and progressive disease [PD], or not evaluable [NE]) from the start of treatment until disease progression, recurrence or end of study. In general, the patient's best response assignment will depend on both the tumor measurement and confirmation criteria.

If an NE response is determined at a time point, this response will be ignored and subsequent non-NE responses will be used for the confirmation. For example, the sequence of tumor assessments: PR, NE, NE, CR, SD, that had more than two consecutive NEs, the third subsequent non-NE response (CR) is used as the confirmation of the first PR for best overall response derivation.

A requirement for SD is that it should be met at least once \geq 6 weeks after the first dose of trial treatment, otherwise the best response will be NE.

The criteria for confirmation of the response are summarized in the following table (Eisenhauer

et al, 2009):

Overall response first time point	Overall response subsequent time point	Best overall response
CR	CR	CR
CR	PR	SD, PD or PR [1]
CR	SD	SD provided minimum criteria for SD duration met, otherwise PD

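### The best-response window has no cut-off at new anticancer therapy and no rule for an irradiated target lesion, and no text says whether permitted palliative radiation ends tumor scans

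*SAP*

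**What the plan says.** **Response window and data source.** In SAP 10.7.1 (Part B, Objective Response), best overall response (BOR) is the best result "from the start of treatment until disease progression, recurrence or end of study". Overall response is "not to be programmatically derived; will be analyzed as collected on eCRF". An NE assessment is skipped and a later non-NE assessment may serve as confirmation. A confirmed response needs at least two consecutive assessments 3 or more weeks apart.

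**Radiation on study.** Protocol 8.6.2 lists among the generally permitted treatments: "Use of localized palliative radiation for pre-existing lesions to control pain, at the discretion of the physician". Protocol 8.6.3 repeats it as an exception to the ban on antineoplastic therapy: "Use of localized palliative radiation for pre-existing lesions to control pain may be allowed at the discretion of the physician". For prohibited treatments it says only that, if one is indicated, "then discontinuation from the study drug may be required".

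**When scans stop.** Protocol Table 9-1, footnote p, schedules scans "until discontinuation of study treatment, disease progression, death, or initiation of further systemic cancer therapy, including radiation therapy, whichever occurs earlier". Protocol Section 10 also ends them at "initiation of further systemic cancer therapy, including radiation therapy". The protocol synopsis and SAP Appendix I carry the same rule.

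**A scan after study drug stops.** Protocol Section 10 states: "Radiology assessment for end of study follow-up and early termination should be performed unless the patient already has radiographic confirmation of progressive disease" (within the preceding 9 weeks). Footnote p words this differently: such a scan is done only if at least 9 weeks have passed since the last scheduled one.

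**What is still reported.** SAP Section 11 keeps ORR in the safety population and the waterfall plot. It drops CBR, DOR and PFS, and also the summaries and listings of concomitant medications.

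**The concern.** A pre-existing lesion can be a target lesion, and eligibility requires only one measurable lesion (Protocol 7.1.1, criterion 5). The irradiated lesion may therefore be the only one that determines response. If the patient stays on OBI-999 and scanning continues, shrinkage from radiation falls inside the SAP window and can be credited to the drug. If the site instead treats the radiation as the end of tumor assessment, a patient still on drug loses response follow-up. The text allows sites to do either.

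The analysis has no safeguard of its own. Overall response is not derived, so no programmed step compares scan dates with treatment dates. The scan-stop rule governs scheduling and does not say which scans count. With concomitant treatments no longer listed, a reader of the abbreviated report might be unable to tell which responses followed radiation.

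**Working it through.** **1. The passages side by side**

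| Question | Answer in the documents |
|---|---|
| Does BOR stop at new anticancer therapy? | No (SAP 10.7.1) |
| Are assessments after target-lesion radiation set to NE or excluded? | No rule in either document |
| May a target lesion be irradiated on treatment? | Not excluded (Protocol 8.6.2, 8.6.3) |
| Does permitted palliative radiation end the scans? | Not stated (synopsis; Table 9-1 footnote p; Section 10; SAP Appendix I) |

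**2. How each route could reach the reported results**

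*Radiation to a target lesion, scans continue.* Scans are 6 or 9 weeks apart, so two consecutive scheduled scans already meet the 3-week separation. Two scans after radiation could give a confirmed PR. One could confirm an earlier PR. One could also set a waterfall bar, because no confirmation is required for that plot.

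*New systemic therapy.* Scheduled scans end at treatment discontinuation or at the new therapy. What can remain is an end-of-study or early-termination scan, with the end-of-study visit 28 ± 7 days after the last dose. One scan is fewer than the two needed. It could confirm an earlier PR or set a waterfall bar, but could not alone make a confirmed response.

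**3. Effect of one miscounted response on ORR**

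- With 9 patients: 0/9 = 0% (Clopper-Pearson 95% CI 0 to 33.6%) becomes 1/9 = 11.1% (0.3 to 48.2%).
- With 11 patients: 1/11 = 9.1%. This assumes that the pancreatic stage 1 was full at 9 and that both replacement patients reported in SAP 5.4 were dosed (9 + 2 = 11). The safety population keeps every dosed patient.

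**4. What it would have meant for the two-stage rule**

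Inputs (SAP Section 7): 9 patients, continue if at least 1 response; 19 in total, success if at least 4; ORR 10% against 25%.

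P(success) = Σ from x = 1 to 9 of C(9,x) pˣ(1−p)⁹⁻ˣ × P(Bin(10,p) ≥ 4−x)

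- p = 0.25: 0.7201, which reproduces the stated 72% power.
- p = 0.10: 0.1100, within the stated one-sided 0.12.
- One miscounted patient in stage 1, the other 18 at p = 0.10: the gate is passed automatically, and P(Bin(18, 0.10) ≥ 3) = 0.266.
- One miscounted patient in stage 2: Σ over x ≥ 1 of P(Bin(9, 0.10) = x) × P(Bin(9, 0.10) ≥ 3−x) = 0.246.
- If a fraction c of drug non-responders were miscounted, the apparent rate is 0.10 + 0.90c. For c = 1%, 2%, 5% and 10%, P(success) is 0.139, 0.172, 0.282 and 0.485. These values of c are assumptions; the documents give none.

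The figures in step 4 describe the design as planned. SAP 5.4 records that the go/no-go analysis did not take place.

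**The case against.** **New therapy is largely handled already.** Progression closes the window, scheduled scans stop at further systemic therapy, other antineoplastic treatment is barred on study, and confirmation needs two assessments. This stands. A reader might infer that new systemic therapy threatens ORR as much as radiation does; the scan schedule does not support that.

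**The radiation passages may not conflict.** The stop refers to further systemic cancer therapy, which can be read as next-line treatment, distinct from local palliation for pain. That reading is reasonable, so a flat contradiction is not shown. The text does not settle it, however, and under this reading scans continue after radiation, which is the case where shrinkage can be miscounted.

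**A false response needs a chain of events.** A target lesion must be irradiated, scanning must continue, shrinkage must reach an overall PR, and the PR must be confirmed. The investigator assigns response under RECIST 1.1 and may enter NE. All true, and it limits the likely frequency. But no instruction tells the investigator to enter NE, and a single NE entry is skipped in favor of later assessments.

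**Nothing was decided on these data.** Correct. The stage-1 gate and the error rates no longer bear on any decision, and lost progression follow-up feeds no retained PFS analysis.

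**A date check cannot find the irradiated lesion.** This also stands. Protocol 8.6.2 asks for dose, regimen, route, indication and dates, but not anatomic site. SAP 10.6.7 specifies radiation field only for prior radiotherapy.

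**Conclusion.** The gap is real, of modest size, and worth closing. The SAP does not cut BOR at new anticancer therapy and does not say how an irradiated target lesion is scored. The protocol leaves open whether the radiation it permits ends tumor assessment. Target-lesion radiation followed by continued scanning is the main route to bias.

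The remaining effect is on two descriptive outputs. One miscounted response adds 11.1 percentage points to a cohort ORR with 9 patients, or 9.1 with 11. The confidence intervals at this size are much wider than the shift, so the harm lies in reporting an activity signal where there was none. The waterfall plot is more exposed, since one scan is enough.

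A reader might infer that the reported ORR is inflated, or that a wrong go decision followed. The documents support neither. They do not say how many patients, if any, had radiation or new therapy before a counted scan, and no go/no-go decision was made.

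**What to change.** 1. In SAP 10.7.1, limit BOR, ORR and the waterfall plot to assessments before the first new anticancer therapy.
2. After on-study radiation to a target lesion, treat assessments as NE for response and leave them out of the waterfall plot.
3. Identify cases from the recorded treatment dates together with the irradiated site. Query the investigational site if the eCRF does not hold the location.
4. List the affected patients in the abbreviated report. If there are none, one sentence saying so settles the matter.
5. Reconcile Protocol 8.6.2 and 8.6.3 with the synopsis, Section 10, Table 9-1 footnote p and SAP Appendix I on whether permitted palliative radiation ends scanning. Which way to resolve it is the sponsor's decision.

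**Cost.** SAP wording, a date check and possibly a few site queries. Sample size, alpha and power do not change.

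**Downside.** A drug response first seen after target-lesion radiation would not count. Nor would a PR seen before radiation but not yet confirmed: under the confirmation table in SAP 10.7.1, a PR followed only by NE becomes SD if the minimum SD duration is met, and otherwise NE. The listing in step 4 lets readers see any such patients.

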**Table 8-1 OBI-999 Dose Modifications for Toxicity**

Toxicity	Hold Dose	% of Full Dose after Recovery to Grade 0-1
Grade 1	Do not hold dose	100
Grade 2	Hold dose until resolution to Grade 0 or 1	75
Grade 3	Hold dose until resolution to Grade 0 or 1	75
Grade 4	Treatment should be discontinued	Not applicable

Once the dose has been reduced for toxicity and found to be well tolerated, re-escalation may be permitted at the Investigator's discretion. If a patient requires dose reductions on more than 2 occasions for toxicity related to OBI-999, the patient should discontinue from the study.

All reasons for treatment modifications should be fully explained.

The study drug dose which is not administered within the permitted window period of  $\pm 3$  days, must be skipped, and the next dose will be administered as per protocol schedule. Any skipped dose due to safety reason and if medically justified, for OBI-999 treatment related or unrelated reasons, will not be captured as a protocol deviation for this study.

Treatment interruption for more than 2 consecutive doses for related or unrelated reasons may necessitate discontinuation of study treatment.

Treatment interruption for intercurrent non-treatment related AEs will be at the Investigator's discretion and based on the well-being of the patient. All reasons for treatment interruption and

delays should be fully explained. Treatment for hematologic and non-hematologic toxicity may be implemented as clinically indicated according to institutional guidelines. Refer Table 8-2 for therapeutic antiemetic and anti-diarrheal recommendations.

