10. ANALYTICAL PLAN AND STATISTICAL METHODS

10.1 GENERAL CONVENTIONS AND STATISTICAL CONSIDERATIONS

All statistical analyses will be performed, and data appendices will be created using the SAS system version 9.4 or higher.

Data collected in this study will be presented in patient data listings and summary tables.

Descriptive statistics (number of patients with non-missing values, mean, standard deviation [SD], median, minimum, and maximum) will be presented for continuous variables. All raw data will be presented to the original number of decimal places. Means and medians will be presented to 1 more decimal place than in the raw data. Standard deviations will be presented to 2 more decimal places than in the raw data. Descriptive summaries of time to event data will include medians and confidence intervals.

All data will be listed for all patients.

Frequency distributions (counts and percentages) together with mean and SD of ordinal scores will be presented for categorical variables. Discrete variables that are ordinal scaled (e.g., Eastern Cooperative Oncology Group [ECOG] performance score) will additionally be presented with mean scores and SD. If not specified otherwise, the number of observations with non-missing values will be the denominator for percentage calculation. Further details on the handling of missing observations are given in section 9.3.

If days are converted to months, a factor of 30.4 days/month will be used. If days are converted to years, a factor of 365.25 days/year will be used. Time will be shown in study weeks, i.e., number of weeks from the first administration of any study drug.

Dose-Escalation (Part A). The dose-escalation analysis will be presented by OBI-999 dose (0.4, 0.8, 1.2, and 1.6 mg/kg) cohorts and overall. The following cohorts and overall will be presented:

- OBI-999 0.4 mg/kg
- OBI-999 0.8 mg/kg
- OBI-999 1.2 mg/kg
- OBI-999 1.6 mg/kg
- Dose-Escalation Total

OBI-999 2.0 mg/kg was planned but Part A was closed before this dose was administered, and therefore there no patients in this cohort. For this reason, this cohort will not be presented in any of the analyses.

Cohort-Expansion (Part B). The expansion part analysis will be presented by cancer type. The following cohorts and overall will be presented:

- Cohort 1: Pancreatic cancer
- Cohort 2: Colorectal cancer
- Cohort 3: Basket (any solid tumor type other than those included in Cohorts 1 and 2)
- Cohort-Expansion Total

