10.2 DEFINITION OF BASELINE, STUDY VISITS, AND VISIT WINDOWS

Baseline for each assessment is defined as the last non-missing assessment prior to first dose of study drug. If scheduled and unscheduled assessments occurred on the same day and they both can qualify for being baseline, the value from the scheduled assessment should be considered as baseline. The baseline will be presented for each part.

The data will be analyzed according to the visits recorded in the eCRF. No additional visit windows will be applied. In listings, any unscheduled visits will be inserted in the appropriate temporal sequence using visit date and time.

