CR	PD	SD provided minimum criteria for SD duration met, otherwise PD
CR	NE for all subsequent time points	SD provided minimum criteria for SD duration met, otherwise NE
PR	CR	PR
PR	PR	PR
PR	SD	SD
PR	PD	SD provided minimum criteria for SD duration met, otherwise PD
PR	NE for all subsequent time points	SD provided minimum criteria for SD duration met, otherwise NE
NE	NE	NE

[1] If a CR is truly met at first timepoint, then any disease seen at a subsequent timepoint, even disease meeting PR criteria relative to baseline, makes the disease PD at that point (since disease must have re-appeared after CR). Best response would depend on whether minimum duration of SD was met. However, sometimes 'CR' may be claimed when subsequent scans suggest small lesions were likely still present and in fact the patient had PR, not CR at the first timepoint. Under these circumstances, the original CR should be changed to a PR and the best response is PR.

Objective Response Rate (ORR) is defined as the percentage of patients with confirmed PR or CR based on tumor assessment as determined by RECIST 1.1 among all the patients in the safety and efficacy populations. A confirmed response will be defined as two or more consecutive assessments separated by at least 3 weeks. For summaries in the safety population, patients who discontinue due to toxicity or clinical progression prior to post-baseline tumor assessments will be considered as non-responders and retained in the denominator. A summary with the number of patients by BOR categories, ORR and the Clopper-Pearson 95% confidence interval (CI) for the ORR will be provided.

A by-patient swim lane plot of time (weeks) to Overall Response will be provided, along with waterfall plots (bar plot) showing the best reduction in target lesion therapy will be presented for Cohort-Expansion patients.

Sample code for ORR is provided below:

```
proc freq data=data;
by cohort;
tables AVAL/binomial alpha=0.05 nocum norow;
exact binomial;
run;
```

If the BOR used for ORR based on unconfirmed and confirmed overall responses differs by 10%, then we will present the same summary for ORR based on unconfirmed overall responses as a sensitivity analysis.

B. Clinical Benefit Rate

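### A compliant first scan can precede the six-week minimum for stable disease, so an evaluable SD may be reported as NE in the best-response counts

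*SAP*

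**What the plan says.** SAP 10.7.1 (Part B, A. Objective Response) derives a BOR for each patient. SD must have been met at least once, at or beyond "6 weeks after the first dose of trial treatment, otherwise the best response will be NE". A table in the same section assigns BOR from a first and a later response. For an unconfirmed CR or PR followed by progression (PD) it gives "SD provided minimum criteria for SD duration met, otherwise PD". Where all later responses are NE it gives "SD provided minimum criteria for SD duration met, otherwise NE". No row starts with SD.

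Scan timing is set in two places:
- Footnote p to Protocol Table 9-1, repeated in SAP Appendix I: "CT or MRI scan will be performed within 1 week prior to the start of the next cycle".
- Protocol Section 10: scans, with a tolerance of 7 days either way, "every 6 weeks for the first 3 months and then every 9 weeks until discontinuation of study treatment".

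Two general conventions bear on how the six weeks are counted. SAP 10.1 says "Time will be shown in study weeks, i.e., number of weeks from the first administration of any study drug". SAP 10.2 says "The data will be analyzed according to the visits recorded in the eCRF. No additional visit windows will be applied". Neither mentions the SD minimum.

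SAP 10.7.1 places the number of patients by BOR category in the same summary as ORR. SAP Section 11 keeps the ORR analysis in the safety population and drops CBR, DOR and PFS from the abbreviated report.

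**The concern.** The SD minimum and the first scheduled scan share the same nominal date, but the scan may be done early and the SD rule has no tolerance. A site that follows the protocol can produce a readable scan showing SD that the SAP then labels not evaluable. The label would reflect scan timing and not disease course. It would also mix such patients with those who truly lacked data: SAP 5.4 reports four patients without a post-baseline RECIST assessment at the end of stage 1 of Part B.

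A second gap concerns early SD followed by PD. The SD sentence sends this sequence to NE. The definition of BOR as the best response until progression, and the table's treatment of early PR followed by PD, both point to PD. Two programmers could code it differently.

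At stake is the split of non-responders among SD, NE and PD. With CBR, DOR and PFS dropped, that split is the main tabulated evidence of disease control left in the report.

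**Working it through.** The plan attaches no computed figure to the SD rule, so there is none to reproduce. Days below are elapsed days after Cycle 1 Day 1.

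1. SD minimum (SAP 10.7.1): 6 × 7 = day 42.
2. Nominal Cycle 3 Day 1 (21-day cycles): 2 × 21 = day 42.
3. First scan under footnote p, nominal dosing: 42 − 7 = 35 to 42 − 1 = 41. All 7 days precede day 42. If a same-day scan counts, the range is 35-42 and 7 of 8 precede it.
4. First scan under Protocol Section 10: 42 ± 7 = days 35-49, which is 15 days. Days 35-41 precede day 42: 7 of 15.
5. Dosing tolerance. The text after Table 8-1 says "The study drug dose which is not administered within the permitted window period of" 3 days either way is skipped. If that window is centred on the nominal schedule, Cycle 3 Day 1 lies on days 39-45. Scans 1-7 days earlier then span 39 − 7 = 32 to 45 − 1 = 44. Days 32-34 comply with footnote p but not with Protocol Section 10, so the two scan rules do not describe the same window.
6. The second scan is nominally day 84, with a window of days 77-91. SD seen there always meets the minimum.

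Effect on BOR with a first scan on day 38:

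| Responses | SAP as written, elapsed time | If a compliant first scan met the minimum |
|---|---|---|
| SD, nothing later | NE | SD |
| SD, then NE | NE | SD |
| SD, then PD | NE by the sentence; PD by the table's fallback | SD |
| PR, then PD | PD | SD |
| PR, then NE | NE | SD |
| SD, then SD | SD | SD |

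To check that nothing else moves, all response sequences of up to three scans were enumerated, with PD ending a sequence: 5 + 4 × 5 + 4 × 4 × 5 = 105. The first scan was set at day 35, 38, 41 or 42, and later scans at days 84 and 147. With the first scan at day 35, 38 or 41, accepting it towards the minimum changes BOR in 15 of 105 sequences. Of these, 11 move from NE to SD under the sentence as written and 4 from PD to SD. With the first scan at day 42, none changes. Responder status changes in 0 of 105 in every case, because ORR counts only confirmed CR or PR and SD, PD and NE are all non-responses. These are counts of possible sequences, not of patients.

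One recoded patient moves a cohort's SD share by 1/9 = 11.1 points. In the pancreatic cohort, if it holds 9 plus the 2 replacements in SAP 5.4, the shift is 1/11 = 9.1 points.

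**The case against.** The strongest reply is that nothing inferential changes. ORR is untouched, the other activity endpoints are dropped, SAP 5.4 records that the go/no-go analysis never took place, and the by-visit response listing in SAP 10.7.1 would still show the SD. This stands, and it sets the low weight of the point. SAP Section 11 does not name BOR and the table shells are in a separate document, so retention of the BOR counts is the natural reading and not an explicit statement.

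The trigger is also narrow: any later qualifying assessment removes the problem. A reader might infer from the day counts above that most patients would be recoded. The documents do not support that. They give no distribution of scan dates and no response sequences, so shares of calendar days are not shares of patients.

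The elapsed-time reading is not certain. The rule's reference to time after first dose favours it. SAP 10.1 lends weaker support, because it is a display convention. SAP 10.2 leaves room for a by-visit reading under which a nominal Week 6 scan would qualify. The SAP also sets no day-count convention for the rule. Its exposure formula in 10.8.1 adds one day; applied here, that would make elapsed day 41 qualify, and 7 of 7 would become 6 of 7 and 7 of 15 would become 6 of 15. The direction survives.

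Finally, a reader might infer that early SD followed by PD is settled as NE. It is not. The table is introduced as giving criteria for confirming a response, so the lack of SD-first rows is not in itself an error, and the BOR definition supports PD. The fault is ambiguity.

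**Conclusion.** The point holds as a low-severity defect of specification. On the elapsed-time reading, a protocol-compliant first scan can precede the SD minimum, and under footnote p with nominal dosing it does so unless a same-day scan is allowed. A patient whose only SD is on that scan is then reported as NE although the scan was evaluable. Early SD followed by PD has no single answer in the SAP.

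The effect is confined to the descriptive SD, NE and PD counts, on the assumption that the BOR summary stays with the retained ORR analysis. The number of patients affected cannot be derived from the documents; each is worth 11 points in a cohort of 9. A reader might go further and infer that the response rate or a stage 1 decision was compromised. The documents do not support this: the enumeration shows no change in responder status, and no go/no-go analysis was done.

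**What to change.** 1. In SAP 10.7.1, state that the SD minimum is met by SD at the first scheduled (Week 6) assessment performed within its protocol window, or by SD at any later assessment. Use the same minimum in every BOR table row that refers to one. Define the window by reference to the reconciled scan schedule and do not write in a fixed day: a day 35 cut-off would still miss scans on days 32-34 that comply with footnote p.
2. Reconcile the scan windows in footnote p (Protocol Table 9-1 and SAP Appendix I) and Protocol Section 10, and say which one defines the Week 6 window.
3. Add two BOR rows: SD then PD, giving SD if the minimum is met and PD if not; and SD then NE or no further assessment, giving SD if the minimum is met and NE if not.
4. Record the change in SAP Section 11 and show the BOR counts under the stated 42-day rule and the window-adjusted rule side by side.

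The cost is one sentence, two table rows and one extra column of descriptive counts in a deliberately short report. SD becomes slightly easier to reach under the adjusted rule, and that rule would be set after an open-label study has stopped. This is why the stated rule should stay visible beside it.
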